4.6.3 Laboratory Data

For clinical laboratory data which are collected from local laboratories, summary statistics will be presented.

4.6.4 Vital Signs

Vital signs will be summarized using mean change from baseline tables over time. Measurements consist of heart and respiratory rate, temperature, and systolic and diastolic blood pressures.

4.7 MISSING DATA

Incomplete dates for AEs, concomitant medication and laboratory data are handled as described in the Roche data analysis standards (GDSR).

Diary cards are used to collect bleeding information post study surgery, either related or unrelated to the study surgery, as well as BPA/FVIII use for any bleeds. Missing information on bleeds are handled as follows:

- If, on a given day, the treatment time is partial and the bleed time complete, the partial time is assumed to be the same as the complete time. In cases of multiple events per day, the last complete time is used.
- All bleeds with an anatomical location in a joint are considered joint bleeds
- All bleeds with missing cause are included as spontaneous bleeds

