### **4.6.2 Patient Discontinuation from Study**

Patients have the right to voluntarily withdraw from the study at any time for any reason. In addition, the investigator has the right to withdraw a patient from the study at any time. Reasons for withdrawal from the study may include, but are not limited to, the following:

- Patient withdrawal of consent at any time
- Any medical condition that the investigator or Sponsor determines may jeopardize the patient's safety if he or she continues in the study
- Investigator or Sponsor determines it is in the best interest of the patient
- Patient's inability or unwillingness to comply with protocol requirements
- Non-compliance despite appropriate education measures taken by the clinical site

Every effort should be made to obtain information on patients who withdraw from the study. The primary reason for withdrawal from the study should be documented on the

appropriate eCRF. However, patients will not be followed for any reason after consent has been withdrawn. Patients who withdraw from the study will not be replaced

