2.2.1 Primary Efficacy Endpoints

- Percentage of patients without excessive bleeding at surgical sites and did not require BPA/FVIII use for bleeding related to the surgery, from the start of the surgery until the patient is discharged from the surgery. For the purposes of this endpoint, the absence of excessive bleeding and BPA/FVIII use will be measured by a good to excellent rating using the hemostatic efficacy scale (ISTH SSC recommendations, see References) and will be determined upon patient discharge by the healthcare professional performing the procedure.

- Percentage of patients with excessive bleeding at surgical sites and required BPA/*FVIII* use for bleeding related to the surgery, from the start of the surgery until the patient is discharged from the surgery. Bleeding and BPA/*FVIII* use will be assessed using the hemostatic efficacy scale and measured by a rating of fair to poor, and will be determined upon patient discharge by the healthcare professional performing the procedure.
 - Dose and schedule (including number of doses, total dose, and frequency) of BPAs/*FVIII* used per bleed for excessive bleeding at surgical sites will be summarized.

- Percentage of patients who, after being discharged from surgery, experienced bleeds that were either related or unrelated to the surgery and also required BPA/*FVIII* use
 - Dose and schedule (including number of doses, total dose, and frequency) of BPAs/*FVIII* used per bleed will be summarized.

Bleeding events and self-administered BPA/*FVIII* use in the third endpoint above are self-reported on the Bleeding and Medication Diary CRF page by patients who undergo the surgical procedure in the study. BPA/*FVIII*, whenever administered by the health care provider, will be obtained and reported by the PI on the Concomitant Medication CRF page.

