4.1.2 Efficacy Analysis Population

All enrolled patients who receive emicizumab and undergo a minor surgery.

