4.4 EFFICACY ANALYSIS

Descriptive statistics along with 95% Clopper Pearson confidence intervals will be used to provide point estimates and precision related to efficacy outcomes. All efficacy analyses will be performed on the efficacy analysis population.

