4.4.1 Primary Efficacy Endpoint

The first 2 primary endpoints listed under section 2.2.1 are composite endpoints from data points collected on the “On-study Targeted Surgery and Procedure Log” CRF page: “Intraoperative and/or postoperative blood loss increased over expectation for the non-hemophilic patient determined at the time of discharge” and “Did the patient use any BPA/*FVIII* for the surgery before the discharge?”.

Primary endpoint 1 is met when response to “Intraoperative and/or postoperative blood loss increased over expectation for the non-hemophilic patient determined at the time of discharge” is “0 to <10%” or “10% to < 25%” AND response to “Did the patient use any BPA/*FVIII* for the surgery before the discharge?” is “No”.

Primary endpoint 2 is met when response to “Intraoperative and/or postoperative blood loss increased over expectation for the non-hemophilic patient determined at the time of discharge” is “25% to <50%” or “>=50%” AND response to “Did the patient use any BPA/*FVIII* for the surgery before the discharge?” is “Yes”.

For the purposes of summarizing the dose and schedule of BPA use per bleed as it relates to primary endpoint 2, BPAs/*FVIII* used for excessive bleeding at surgical sites are reported by the investigator and captured in “Concomitant Medications” CRF.

Primary endpoint 3 is also a composite endpoint based on information collected in “Bleed and Medication Diary” and “Concomitant Medications” CRFs.

For primary endpoint 3, bleeding information is self-reported by patients (or patient’s legally authorized representative) on the “Bleed and Medication Diary” and transcribed into the “Bleed and Medication Diary” CRF page. BPAs/*FVIII* used to treat excessive bleeding are also self-reported by patients if they are administered by the patients. BPAs/*FVIII* administered by the investigators to treat the bleeding will be reported on the “Concomitant Medications” CRF page.

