4.4.3 Exploratory Efficacy Endpoints

As an exploratory efficacy endpoint, the percentage of patients with zero bleeds (regardless of treated or not) after being discharged from surgery will be summarized separately for the inhibitor and non-inhibitor cohorts and will be displayed overall and by surgery type.

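### The SAP does not say how to score an operated patient with absent or incomplete post-discharge follow-up; by default endpoint 3 counts that patient as a non-event

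*SAP*

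**What the plan says.** **Denominator.** SAP 4.1.2 defines the efficacy population as "All enrolled patients who receive emicizumab and undergo a minor surgery", and SAP 4.4 states that "All efficacy analyses will be performed on the efficacy analysis population". Neither asks for any post-discharge data.

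**Endpoint 3.** SAP 2.2.1 defines it as "Percentage of patients who, after being discharged from surgery, experienced bleeds that were either related or unrelated to the surgery and also required" BPA or FVIII. Under SAP 4.4.1, "bleeding information is self-reported by patients" in the diary, and treatment given by the investigator comes from the Concomitant Medications CRF. For endpoints 1 and 2 that section states exactly which CRF answers meet the endpoint. For endpoint 3 it only names the data sources.

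**Related outputs.** SAP 4.4.3 summarises "the percentage of patients with zero bleeds (regardless of treated or not) after being discharged from surgery". SAP 4.4.4 tabulates patients with 0, 1, 2, 3 or more than 3 treated bleeds and has no row for unknown.

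**Missing data.** SAP 4.7 says "Missing information on bleeds are handled as follows" and gives three rules, on partial treatment times, joint location and missing cause. The sponsor's data standard is cited only for incomplete dates of adverse events, concomitant medication and laboratory data.

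**Follow-up.** The diary is four weekly cards (Protocol 4.5.5). There are calls on Days 2, 3 and 28 and a visit on Day 8 (Protocol 3.1, SAP 2). Patients who withdraw are not replaced, and "patients will not be followed for any reason after consent has been withdrawn" (Protocol 4.6.2).

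**The concern.** All three rules in SAP 4.7 work on a bleed that someone has recorded. None deals with a patient for whom nothing was recorded because the diary was not returned and contacts were missed, or because the patient left early. That patient stays in the denominator, since surgery took place, and cannot enter the endpoint 3 numerator, since no bleed is on file. Lack of information then reads as a good outcome for one of the three primary endpoints and in the treated-bleed distribution.

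The study tests no hypothesis, so no error rate is at risk. The point estimates and their exact intervals are the whole result, however, and the rule that produces them should be written down. Early termination with limited sample sizes (SAP 2.2.3) gives each unobserved patient more weight.

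**Working it through.** **Plan's own figures.** Clopper-Pearson limits for x events in n are the 2.5% quantile of Beta(x, n−x+1) and the 97.5% quantile of Beta(x+1, n−x). All six rows of the SAP 2.3 precision table reproduce to three decimals (for example, 2/20 gives 0.012 to 0.317 and 6/20 gives 0.119 to 0.543).

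**Inputs.** n = 20 is the lower end of the planned cohort size (SAP 2.3). The 2 treated bleeders in 20 and 6 bleeders of any kind in 20 are taken from that table's illustrative rows. The number with no post-discharge data, m, is not in the documents; I assume m = 2 and then vary it from 1 to 4.

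**Endpoint 3**, with x recorded treated bleeders:
- default, x/n: 2/20 = 10.0% (95% CI 1.2 to 31.7)
- observed patients only, x/(n−m): 2/18 = 11.1% (1.4 to 34.7)
- upper bound, (x+m)/n: 4/20 = 20.0% (5.7 to 43.7)

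The two bounds differ by m/n whatever x is. Each unknown patient is worth 1/20 = 5 points at n = 20 and 1/30 = 3.3 points at n = 30.

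| n | x | m | Default | Observed only | Upper bound |
|---|---|---|---|---|---|
| 20 | 2 | 1 | 10.0% | 10.5% | 15.0% |
| 20 | 2 | 4 | 10.0% | 12.5% | 30.0% |
| 30 | 3 | 1 | 10.0% | 10.3% | 13.3% |
| 30 | 3 | 4 | 10.0% | 11.5% | 23.3% |
| 10 (assumed, after early termination) | 1 | 2 | 10.0% | 12.5% | 30.0% |

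**Zero-bleed rate**, with b recorded bleeders, n = 20, b = 6, m = 2:
- absence of a record taken as zero bleeds, (n−b)/n: 14/20 = 70.0% (45.7 to 88.1)
- observed patients only, (n−b−m)/(n−m): 12/18 = 66.7% (41.0 to 86.7)
- unobserved patients left out of the numerator, (n−b−m)/n: 12/20 = 60.0% (36.1 to 80.9)

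Two programmers could follow SAP 4.4.3 and report 70.0% or 60.0% from the same data.

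**Direction.** In every scenario above, the default gives the lowest endpoint 3 rate, and reading no record as zero bleeds gives the highest zero-bleed rate.

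**The case against.** The strongest reply is that the SAP nowhere equates missing with no bleed. That is right, and a reader who infers a stated rule goes further than the text. For endpoint 3 the default follows from a fixed denominator and a numerator of recorded events. For the zero-bleed rate even that does not settle it, because an unobserved patient could equally be left out of the numerator.

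A reader might also infer that an unreturned card means no data. The documents do not support that. Four scheduled contacts collect information on bleeding or its treatment. Protocol 4.4 has medications, including BPA and FVIII, reported at each contact and captured in the eCRF. Protocol 4.6.2 asks for every effort to obtain information on withdrawn patients, and its bar on further follow-up applies once consent is withdrawn. What remains is that SAP 4.4.1 takes bleed information from the diary and never says when contact data may stand in for a missing card.

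Third, the effect may be small. In the main illustration the default and observed-only rates differ by 11.1 − 10.0 = 1.1 points, with similar intervals; the 10-point gap appears only if every unobserved patient bled and was treated. This stands as a limit on size.

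Finally, SAP 4.2 summarises discontinuations by cohort and surgery type and lists the reasons, and SAP 4 allows listings if data are sparse. That would show early withdrawals. It would not show incomplete diaries among completers, and it does not connect withdrawal to how endpoint 3 is scored.

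**Conclusion.** The gap is real and nothing elsewhere in the documents closes it. For endpoint 3 and the SAP 4.4.4 table, an operated patient without post-discharge data becomes a non-event by default, which favours the drug. For the zero-bleed rate the scoring is undefined, with a likely favourable default.

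The documents give no number missing, so the size can only be illustrated. With 2 of 20 unobserved and 2 recorded treated bleeders, endpoint 3 is 10.0% by default and at most 20.0%, with 11.1% among observed patients. A reader might infer that the reported rates will be badly biased; the documents do not support that, since follow-up is 28 days with several contacts and few patients may be affected. The point deserves correction because it touches a primary endpoint and costs little to settle.

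**What to change.** Amend SAP 4.4.1, 4.4.3, 4.4.4 and 4.7 to state:
- A recorded post-discharge bleed from any source (diary, scheduled contact or Concomitant Medications CRF) counts as an event however short the follow-up. For endpoint 3 this means a bleed treated with BPA or FVIII; for the zero-bleed rate, any bleed.
- A patient counts as bleed-free only if diary cards or scheduled contacts together cover discharge through the Day 28 contact.
- Every other operated patient is unknown.

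Add an unknown row to the SAP 4.4.4 table and report the number unknown per cohort. Show endpoint 3 and the zero-bleed rate on the full efficacy population twice, with unknowns counted first as non-events and then as events (for the zero-bleed rate, an event is a bleed).

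A complete-case rate alone should not replace these two figures. It would keep incompletely followed patients who bled and drop incompletely followed patients who did not, which biases the bleed rate upward.

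The cost is SAP wording, a few extra table rows and a possibly less favourable range. No new data are needed.

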4.8 INTERIM ANALYSES

Not applicable.

Appendix 1 Protocol Synopsis

PROTOCOL SYNOPSIS

TITLE: A PHASE IV, MULTICENTER, SINGLE-ARM, OPEN-LABEL STUDY OF EMICIZUMAB PROPHYLAXIS IN PATIENTS WITH HEMOPHILIA A *WITH OR WITHOUT* INHIBITORS UNDERGOING MINOR SURGICAL PROCEDURES

PROTOCOL NUMBER: ML39791

VERSION NUMBER: 4

EUDRACT NUMBER: Not applicable

IND NUMBER: 122954

TEST PRODUCT: Emicizumab (HEMLIBRA®)

PHASE: Phase IV

INDICATION: Hemophilia A with *or without* inhibitors

SPONSOR: Genentech, Inc.

Objectives and Endpoints

This study will evaluate the safety and efficacy of emicizumab prophylaxis in patients with hemophilia A (PwHA; *with or without* inhibitors) *that are* undergoing minor surgical procedures *without additional prophylaxis with bypassing agents (BPA; for patients with inhibitors) or factor VIII (FVIII; for patients without inhibitors)*. All endpoints will be measured and described separately for the inhibitor and non-inhibitor cohorts. Pharmacokinetics will also be evaluated as exploratory objectives of the study. For the purposes of this protocol, study treatment is not intended to imply that the Sponsor is providing the study drug; rather, emicizumab is required for all patients during the study per the inclusion and exclusion criteria.

Note: Throughout the protocol, all references to BPA will be specific for patients with inhibitors and all references to FVIII will be specific for patients without inhibitors, unless otherwise noted.

Primary Objective	Corresponding Endpoints

 To evaluate the efficacy of emicizumab in preventing surgery-related bleeding in PwHA with and without inhibitors undergoing minor surgical procedures 	
Efficacy will be measured by:
 
 Percentage of patients without excessive bleeding at surgical sites and did not require BPA/FVIII^a use for bleeding related to the surgery, from the start of the surgery until the patient is discharged from the surgery. For the purposes of this endpoint, the absence of excessive bleeding and BPA/FVIII^a use will be measured by a good to excellent rating using the hemostatic efficacy scale (ISTH SSC recommendations) and will be determined upon patient discharge by the healthcare professional performing the procedure. Percentage of patients with excessive bleeding at surgical sites and required BPA/FVIII^a use for bleeding related to the surgery, from the start of the surgery until the patient is discharged from the surgery. Bleeding and BPA/FVIII^a use will be assessed using the hemostatic efficacy scale and measured by a rating of fair to poor, and will be determined upon patient discharge by the healthcare professional performing the procedure. 
 Dose and schedule (including number of doses, total dose, and frequency) of BPAs/FVIII^a used per bleed for excessive bleeding at surgical sites will be summarized. Percentage of patients who, after being discharged from surgery, experienced bleeds that were either related or unrelated to the surgery and also required BPA/FVIII^a use 
 Dose and schedule (including number of doses, total dose, and frequency) of BPAs/FVIII^a used per bleed will be summarized

 Safety 	
 Incidence and severity of all adverse events 
 Incidence and severity of serious adverse events Incidence and severity of adverse events of special interest Percentage of patients with surgical complications requiring hospitalization or return to surgery Percentage of patients who need blood/blood product transfusions (i.e., platelets, plasma, etc.) during surgery
Exploratory Objective	Exploratory Endpoints

 To evaluate potential relationships between drug exposure and the efficacy and safety of emicizumab 	
 Selected efficacy and safety endpoints will be descriptively summarized by plasma emicizumab concentration levels

 To describe the incidence of spontaneous bleeding in the post-operative period. 	
 Percentage of patients with zero bleeds (regardless of treated or not) after being discharged from surgery

BPA= bypassing agent; ISTH SSC= International Society on Thrombosis and Haemostasis Scientific and Standardization Committee; FVIII = factor VIII; PwHA= patients with Hemophilia A.

^a BPA use is specific for patients with inhibitors and FVIII use is specific for patients without inhibitors.

Study Design

Description of Study

This Phase IV, multicenter study will evaluate whether PwHA (*with or without inhibitors*) receiving emicizumab prophylaxis can safely undergo minor surgical procedures without additional prophylaxis *with BPA or FVIII (for patients with or without inhibitors, respectively)*. The use of BPA/FVIII for excessive surgical bleeding will then be measured intra-operatively and post-operatively. In addition, surgical complications from bleeding and blood product transfusions will be evaluated. This study will assess emicizumab prophylaxis alone to control surgery-related bleeding in PwHA *with or without inhibitors* undergoing minor surgical procedures. *Each cohort (PwHA with inhibitors and PwHA without inhibitors) will be assessed separately.*

Patients can be screened and enrolled up to 60 days prior to surgery. They must have received a minimum of four loading doses of emicizumab prior to their surgical procedure, been adherent with emicizumab prophylaxis, and must not have received BPA/FVIII for at least 24 hours prior to surgery. In addition, they must plan to continue emicizumab prophylaxis for at least 1 month after the surgical procedure. Follow-up will be conducted by phone on Study Days 2 and 3 (approximately 24 and 48 hours post-operation) to record any bypassing agent use or FVIII use and surgical bleeding within the first 48 hours, as well as treatment of any other bleeding unrelated to surgery. BPA/FVIII should only be used for treatment of bleeding. Follow-up will be conducted in person on Study Day 8 (± 2 days) to examine the patient for any post-surgical complications and to collect information on treatment of bleeding. Lastly, follow-up will be conducted by phone on Study Day 28 (± 2 days) to record any surgical complications, bleeds, and/or use of BPA/FVIII.

Blood samples will also be collected in this study for observational purposes and will not be used to determine eligibility or treatment decisions. Samples will be used to evaluate emicizumab concentration (PK) prior to surgery.

Safety follow-up will be conducted after signing the informed consent form. Patients will be monitored for adverse events to evaluate the safety of emicizumab alone or in combination with BPA/FVIII.

Periodic Safety Review

In order to ensure that patients enrolled in this study are safely undergoing minor surgical procedures without additional pre-operative prophylaxis with BPAs/FVIII, periodic safety assessments are planned. The study team will perform periodic data review of all available data.

Number of Patients

Approximately 40–60 PwHA (*approximately 20–30 patients with inhibitors and 20–30 patients without inhibitors*) will be enrolled and undergo a minor surgical procedure at approximately 20 sites in the United States. An effort will be made to ensure enrollment between multiple surgery types. A maximum of 9 patients *in each cohort* will be enrolled in any given surgery type.

Target Population

Inclusion Criteria

Patients must meet the following criteria for study entry:

- Signed Informed Consent/Assent Form
- *Any age (newborn and older)*
- Ability to comply with the study protocol, in the investigator's judgment
- Diagnosis of hemophilia A and current or history of *an inhibitor (Bethesda titer ≥ 0.6 Bethesda units) and currently using BPA for breakthrough bleeds (for PwHA with inhibitors)*
- *Diagnosis of hemophilia A and no history of an inhibitor (Bethesda titer < 0.6 Bethesda units), or a history of an inhibitor that has been tolerized for > 5 years and using FVIII for breakthrough bleeds (for PwHA without inhibitors)*

- Plan to receive at least 4 loading doses of emicizumab and been adherent to emicizumab prophylaxis by the time of the surgery
- Undergoing minor surgery within 60 days of study enrollment. Other minor surgical procedures could be included upon consultation and approval of Medical Monitor, but examples include (see Appendix 3 for a full list):
 - Central venous catheter insertion/removal/replacement
 - Simple dental extractions
 - Colonoscopy, cystoscopy, or endoscopy with biopsy
 - Excisional skin biopsy
- Must plan to continue emicizumab prophylaxis for at least 1 month after surgery
- For women of childbearing potential: agreement to remain abstinent (refrain from heterosexual intercourse) or use contraceptive methods that result in a failure rate of < 1% per year during the study period
 - A woman is considered to be of childbearing potential if she is post-menarchal, has not reached a postmenopausal state (≥ 12 continuous months of amenorrhea with no identified cause other than menopause), and has not undergone surgical sterilization (removal of ovaries and/or uterus).
 - Examples of *highly effective* contraceptive methods with a failure rate of < 1% per year include *proper use of combined oral or injected hormonal contraceptive, bilateral tubal ligation, male sterilization, hormone-releasing intrauterine devices, and copper intrauterine devices.*
 - The reliability of sexual abstinence should be evaluated in relation to the duration of the clinical trial and the preferred and usual lifestyle of the patient. Periodic abstinence (e.g., calendar, ovulation, symptothermal, or post-ovulation methods) and withdrawal are not acceptable methods of contraception.

Exclusion Criteria

Patients who meet any of the following criteria will be excluded from study entry:

- Diagnosis of a bleeding disorder other than hemophilia A
- Tolerized to Factor VIII products (*for PwHA with inhibitors*)
- *Using FVIII products to treat breakthrough bleeds (for PwHA with inhibitors)*
- *Tolerized to FVIII products for <5 years (for PwHA without inhibitors)*
- Treatment with bypassing agents *or FVIII* within 24 hours prior to surgical procedure
- Undergoing a major surgical procedure
- Previous (in the past 12 months) or current treatment for thromboembolic disease (with the exception of previous catheter-associated thrombosis for which anti-thrombotic treatment is not currently ongoing) or current signs of thromboembolic disease
- Other conditions (e.g., certain autoimmune diseases, including, but not limited to diseases such as systemic lupus erythematosus, inflammatory bowel disease, and antiphospholipid syndrome) that may increase the risk of bleeding or thrombosis
- Patients who are at high risk for thrombotic microangiopathy (TMA; e.g., have a previous medical or family history of TMA), in the investigator's judgment
- Would refuse treatment with blood or blood products, if necessary.
- Any serious medical condition or abnormality in clinical laboratory tests that, in the investigator's judgment, precludes the patient's safe participation in and completion of the study
- Pregnant or lactating, or intending to become pregnant during the study
 - Women of childbearing potential must have a negative serum pregnancy test result within 7 days before Study Day 1

- Treatment with any of the following:
 - An investigational drug to treat or reduce the risk of hemophilic bleeds within 5 half-lives of last drug administration before Study Day 1
 - A non-hemophilia-related investigational drug within the last 30 days or 5 half-lives before Study Day 1, whichever is longer
 - An investigational drug concurrently
- History of clinically significant hypersensitivity associated with monoclonal antibody therapies or components of the emicizumab injection
- Known HIV infection with CD4 count < 200 cells/ μ L within 24 weeks prior to *enrollment*

End of Study

The end of this study is defined as the date when the last patient, last visit (LPLV) occurs or the date at which the last data point required for statistical analysis or safety follow-up is received from the last patient, whichever occurs later. The end of a patient's participation in the study is expected to occur after Study Day 28.

Length of Study

The total length of the study, from *enrollment* of the first patient to the end of the study (last patient last visit), is expected to be approximately 24–30 months.

Emicizumab

If a patient is prescribed emicizumab for prophylaxis, emicizumab is administered 3 mg/kg/week subcutaneously for the first 4 weeks when initiating treatment (loading doses), followed by 1.5 mg/kg/week subcutaneously or by any other approved maintenance regimen. Patients must have received all loading doses and been adherent to emicizumab prophylaxis prior to surgery and plan to continue emicizumab for a minimum of 1 month after surgery. For the purposes of this protocol, study treatment is not intended to imply that the Sponsor is providing the study drug; rather, emicizumab is required for all patients during the study per the inclusion and exclusion criteria.

Statistical Methods

Analysis

This is an open-label, single-arm, multicenter study to evaluate emicizumab prophylaxis in PwHA *without inhibitors* and PwHA *with inhibitors*, who are undergoing minor surgical procedures. *Each cohort will be evaluated separately.* No statistical hypothesis will be tested. There are three populations that will be included in the analyses, which are defined as follows:

- All Enrolled Population: All patients who sign informed consent.
- Safety Analysis Population: All enrolled patients who receive emicizumab
- Efficacy Analysis Population: All enrolled patients who receive emicizumab and undergo a minor surgery.

Only descriptive summaries will be presented for data collected in this study. Continuous variables will be summarized using means, standard deviations, medians, and ranges; categorical variables will be summarized using proportions, and 95% confidence intervals where applicable, as appropriate. Additional details of the analyses will be presented in the statistical analysis plan.

Determination of Sample Size

The sample size for this study is based on clinical rather than statistical considerations, taking into account the limited number of inhibitor patients with a planned minor surgery available for participation in this study. Table 5 illustrates the precision of this study for a binary efficacy endpoint assuming a total of approximately 20–30 patients *per cohort* enrolled into this study, received emicizumab, and underwent a protocol-specified minor surgery.

During the study, a re-assessment of the initially specified sample size may be performed. This may result in an increase in sample size, if necessary, to expand the safety database.

